In a hypothesis testing research proposal, briefly mention the hypothesis to be tested and provide the scientific basis of the hypothesis, critically examining the observations leading to the formulation of the hypothesis.

Does this research proposal involve testing of hypothesis: No Yes (describe below)

Does this research proposal involve testing of hypothesis: No Yes (describe below)

- Vaccination of women of childbearing age with Hecolin will decrease HEV disease incidence and thus HEV-related complications among vaccinated pregnant women and their children.
- Hecolin is safe and immunogenic in women of childbearing age.
- Hecolin is effective in protecting against HEV genotype 1.
- Vaccination of women against HEV is feasible, acceptable and cost-effective in low-income countries.
- Dried blood spot and salivary samples (approx 2 ml) are suitable for diagnosing HEV infections and evaluating immunity against HEV.
- High viral load, abnormal immune response, and certain subtypes of HEV are all risk factors for serious disease.

Specific Objectives:

Describe the specific objectives of the proposed study. State the specific parameters, gender aspects, biological functions, rates, and processes that will be assessed by specific methods.

Primary objectives:

- To determine the effectiveness of hepatitis E virus (HEV) vaccine given in women of child bearing age in preventing HEV disease during pregnancy among women in rural Bangladesh

Primary endpoint: confirmed- HEV diseases among pregnant women

Secondary objectives:

- To determine the safety and immunogenicity of HEV vaccine in Bangladeshi women of childbearing age
- To measure the effectiveness of HEV vaccine in preventing HEV disease in non-pregnant Bangladeshi women of childbearing age
- To estimate serological correlates of protection
- To assess the feasibility, acceptability and cost-effectiveness of HEV vaccination of women of childbearing age in rural Bangladesh
- To investigate acute HEV cases virologically, clinically and immunologically in relation to outcome.
- To analyze the persistence of vaccine induced serum antibody responses

Secondary endpoint: Safety, immunogenicity, confirmed HEV diseases in non-pregnant women, viral load and subtypes/mutations, altered immune response, maternal and perinatal mortality associated with maternal jaundice, operational challenges in the delivery of the vaccine and acceptance of vaccine by the users.

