All cases of acute hepatitis will be investigated both clinically and by laboratory diagnostics for the presence of markers of viral hepatitis (A, B, C or E). The clinical symptoms and signs included and the laboratory analyses are described in SOP and will include diagnostics for confirmation of HEV.

Laboratory work will be conducted both in Bangladesh and Norway. All blood samples will be transported to the Matlab hospital. icddr,b laboratory will perform ELISA tests for HEV and HEV PCR as well as other analyses. In addition biochemical parameters with possible relation to vaccine response or failure and HEV infection will be analysed. Samples from the acute hepatitis cases will be transported to the Department of Virology at NIPH for further characterisation. Thus, the samples will be sent abroad and will be stored for 5 years.

During pre-testing 10 participants (among 100 participants) and during main study 50 participants (among 20,745 participants) will be selected randomly for blood collection (9 ml) before and 1 month after last vaccine dose. We need to validate DBS method with plasma samples using ELISA. We will compare the results and confirm that DBS method is suitable for HEV antibody testing (IgG and IgM) as conducted by using direct plasma samples. During main study these results (PBMC and DBS etc) will also be compared with acute hepatitis cases.

In this sub-study another whole blood sample (3 ml) will be collected 2 years (24 to 35 months) after the last dose (dose 3) for those who completed full schedule and also who received 1 or 2 doses of vaccine (incomplete schedule).

Laboratory Methodology

HEV RNA detection method: Viral RNA will be extracted using QIAamp viral RNA extraction kit (Qiagen, Hilden, Germany). HEV RNA will be detected using real time PCR. Negative and positive controls will be included in each run. For details, see the latest version of the Lab Analysis Plan.

Surveillance

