A blood sample will be taken from all participants at baseline and one month after the last dose of the vaccine. Paired specimens from each individual will be tested together. Seroconversion will be determined using ELISA method (Zhu et al, 2010) and the rates will be compared between recipients of HEV vaccine and HBV vaccine. Serological immune correlates of protection will be determined by two methods: 1) comparing post-HEV vaccination titres in recipients of a complete regimen of HEV vaccine who develop HEV disease versus recipients who do not 2) the method which estimates protective level of antibodies by comparing the relative risk of the disease outcome using the reverse cumulative distribution curves of antibody responses in vaccinees and comparison group participants (Klugman 1996).

Titers of serum IgG anti-HEV antibodies, as well as of different isotypes for IgG (G1-G4) of these antibodies will be determined (following Wantai kit guidelines, China) at the different time points (baseline day 0, 1 month after dose 3 and at 2 years (24 to 35 months) after dose 3 or who received 1 or 2 doses).

Evaluation of specimen types for acute hepatitis cases

The feasibility of using dried blood spots (DBS) for detection of HEV RNA and HEV antibodies will be evaluated (Lee CE et al, 2011; Mohamed S et al, 2013) taking into account storage conditions (time and temperature) and sensitivity. EDTA-plasma, capillary blood on DBS and saliva samples (approx 2 ml) from 50 participants with established active HEV infection and 50 vaccinated participants will be collected for this project. Standard HEV ELISA anti-HEV IgM/IgG and PCR will be optimised and evaluated for the different types of material using plasma samples as gold standard.

Evaluation of risk factors and the natural course of HEV disease

A blood and stool sample will be collected from jaundiced patients. If HEV disease is confirmed by the presence of anti HEV IgM or HEV RNA, blood samples will be analysed for relevant biochemical, microbiological and immunological markers. This include viral load, HEV subtypes, other hepatitis infections, antibody titer, cellular response, cytokines, alanine transaminase (ALT), INR and albumin.. The patients symptoms and signs will be recorded regularly during the disease by health workers.

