The Norwegian Institute of Public Health (NIPH) is a driving force in improving the health, quality of life and legal protection of the population. NIPH a wide range of internationally recognized scientific expertise reflected in participation in 26 projects in FP7 and an ERC grant in 2013. The NIPH also collaborates with the WHO, EU, EEA, sister institutions, universities, organizations and health authorities in low and middle income countries on global health issues. The NIPH is currently involved in several vaccine-trials abroad and nationally, including Ebola vaccine in Guinea, meningococcal vaccine in Ethiopia and rotavirus vaccine in India and Norway.

Incepta Pharmaceuticals- Established in 1999, one of the largest pharmaceutical industry is involved in producing vaccine and drugs.

Xiamen University and Inovax Biotech in China developed HEV 239 (Hecolin™) vaccine.

ideSHi- Optimization and validation of DBS ELISA will be performed from samples of HEV patient's serum those are being collected for completion of PhD Project of [name], who is working at our collaborating institute ideSHi. These optimization and validation of the assay will be performed in both places and is very much needed for understanding and assay of samples of vaccine participants from HEV pilot project. Optimization and validation of the DBS ELISA assay will help to conduct a large scale study to see the vaccine efficacy and thus help to prevent maternal and perinatal mortality.

Facilities Available

Describe the availability of physical facilities at site of conduction of the study. If applicable, describe the use of Biosafety Level 2 and/or 3 laboratory facilities. For clinical and laboratory-based studies, indicate the provision of hospital and other types of adequate participant care and laboratory support services. Identify the laboratory facilities and major equipment that will be required for the study. For field studies, describe the field area including its size, population, and means of communications plus field management plans specifying gender considerations for community and for research team members.

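### For saliva and for HEV RNA PCR on dried blood spots, assays are optimised and evaluated on one named collection with no separation or correction, so accuracy against plasma may be overstated

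*Combined protocol and SAP*

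**What the plan says.** The hypothesis list (Hypothesis to be tested) includes that "Dried blood spot and salivary samples (approx 2 ml) are suitable for diagnosing HEV infections and evaluating immunity against HEV".

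Under Evaluation of specimen types for acute hepatitis cases, plasma, capillary DBS and saliva "from 50 participants with established active HEV infection and 50 vaccinated participants will be collected for this project". The feasibility of DBS is to be judged "taking into account storage conditions (time and temperature) and sensitivity". The next step is: "Standard HEV ELISA anti-HEV IgM/IgG and PCR will be optimised and evaluated for the different types of material using plasma samples as gold standard". No cut-off rule, acceptance threshold, hold-out or resampling is given.

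Two other places concern the DBS antibody ELISA only:

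- Biological sampling: 10 pretest and 50 main-study participants "will be selected randomly for blood collection (9 ml) before and 1 month after last vaccine dose". The text continues "We need to validate DBS method with plasma samples using ELISA" and then "We will compare the results and confirm that DBS method is suitable for HEV antibody testing", for IgG and IgM.
- Collaborative Arrangements (ideSHi): "Optimization and validation of DBS ELISA will be performed from samples of HEV" patients' serum collected for a separate doctoral project. The work is described as needed for assaying the pilot samples.

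Biological sampling also plans blood and saliva from any participant who presents with acute hepatitis, but does not assign these specimens to assay evaluation. Laboratory detail is deferred to a Lab Analysis Plan, cited under HEV RNA detection, which is not among the documents.

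**The concern.** Optimising an assay for a new specimen type can mean choosing elution, dilution, storage handling or a positivity cut-off. If any of these is chosen because it agrees best with plasma, and agreement is then reported on the same specimens, the choice has exploited chance features of those specimens. The reported sensitivity and specificity then tend to be higher than new patients would show.

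What is at stake is the suitability hypothesis. The rationale presents saliva as a potential alternative to blood where sampling and cold transport are hard, and says that little is known about HEV antibodies in saliva. An optimistic figure could help carry a specimen type into use that performs less well than reported.

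**Working it through.** The plan states no expected accuracy, precision or threshold for this work, so there is no figure to reproduce. The check has two parts.

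**1. Which samples are named for which step**

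| Specimen and assay | Samples assigned | Separation of optimisation from evaluation |
|---|---|---|
| Saliva, all assays | 50 infected + 50 vaccinated | None stated |
| DBS, HEV RNA PCR | 50 infected + 50 vaccinated | None stated |
| DBS, antibody ELISA | ideSHi sera; 10 pretest + 50 main-study participants; 50 infected + 50 vaccinated | Several sets exist. The ideSHi sera serve both optimisation and validation, and no lock is stated before participants are tested |

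The first two rows carry the concern. The third is a narrower gap in sequence.

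**2. How large the bias could be**

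Input from the plan: 50 + 50. Everything else is assumed. The readout is normal with SD 1 in both groups, with mean 0 in negatives and d in positives. At cut-off c:

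- sensitivity = 1 − Φ(c − d)
- specificity = Φ(c)
- balanced accuracy = (sensitivity + specificity)/2
- Youden's J = sensitivity + specificity − 1, so a difference in J is twice the difference in balanced accuracy
- AUC = Φ(d/√2)

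In each simulated study the cut-off maximises J on the 50 + 50. The apparent value is then compared with the true value at that cut-off.

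*Cut-off only, by separation (2,000 runs each):*

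| d | AUC | Apparent | True | Overstatement (points) |
|---|---|---|---|---|
| 2 | Φ(1.41) = 0.92 | 0.864 | 0.833 | 3.1 |
| 3 | Φ(2.12) = 0.98 | 0.948 | 0.926 | 2.2 |
| 4 | Φ(2.83) = 0.998 | 0.986 | 0.973 | 1.3 |

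As a check, the best attainable value is Φ(d/2), which is 0.841, 0.933 and 0.977. The true values sit just below these, as they should.

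*Cut-off only, weaker assays (4,000 runs), J halved to balanced accuracy:*

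- AUC 0.80: (0.508 − 0.428)/2 = 4.0 points
- AUC 0.85: (0.591 − 0.517)/2 = 3.7 points
- AUC 0.90: (0.682 − 0.618)/2 = 3.2 points
- AUC 0.95: (0.794 − 0.739)/2 = 2.8 points

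Tuning only a cut-off therefore costs about 1 to 4 points.

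*Best of several handling conditions as well as the cut-off:*

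- Best of four, assumed correlation 0.7: AUC 0.85, (0.643 − 0.521)/2 = 6.1 points; AUC 0.90, (0.729 − 0.622)/2 = 5.4; AUC 0.95, (0.836 − 0.744)/2 = 4.6.
- Best of five, simulated as independent and so an upper bound for five: 6.6, 4.3 and 2.4 points at d = 2, 3 and 4.

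*Precision.* Exact 95% intervals are 78.2% to 96.7% for 45/50 and 86.3% to 99.5% for 48/50. Halving the collection would widen this: 24/25 gives 79.6% to 99.9%. A simple split is therefore a poor way to separate the two steps.

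**The case against.** Several objections have force.

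- **Tuning is inferred.** The plan does not say that a cut-off will be tuned or that the same individual specimens serve both steps. It speaks of standard assays, and serum IgG testing follows a commercial kit's guidelines. If kit cut-offs are kept and no condition is chosen on agreement, the bias could be near zero. The Lab Analysis Plan might settle this. This stands: the documents support a risk of bias, not a finding that the results are biased.
- **DBS antibody ELISA.** A reader might infer that the whole DBS and saliva programme rests on the 50 + 50. The documents do not support that: the DBS antibody ELISA has the ideSHi sera and the 10 + 50 random participants, and its suitability conclusion is tied to the latter comparison. What remains is that the ideSHi sera are named for both steps and no lock is stated.
- **Saliva elsewhere.** A reader might also infer that no other saliva will exist. In fact saliva is planned from all acute hepatitis cases, some of which may be HEV-negative. But those cases may be the source of the 50 infected, and the plan does not assign them to evaluation.
- **The simulation fits imperfectly.** The vaccine given to the 50 vaccinated participants is not stated. If it was HEV vaccine, the 98–100% seroconversion cited in the background makes them IgG positives, so a 50-negative model would not apply to IgG. A two-normal score is also a rough model for real-time PCR. The figures show an order of magnitude only.
- **Sampling error is larger than the cut-off bias.** That is true, but a confidence interval around an optimistic estimate does not remove an error that runs in one direction.
- **Low stakes for the trial.** DBS and saliva appear in no listed objective or endpoint, and the primary endpoint rests on serum ALT, serum antibodies and HEV RNA. This stands and limits the severity.

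**Conclusion.** The point holds for saliva (all assays) and for HEV RNA PCR on DBS. One collection is assigned to both optimisation and evaluation, and no separation or correction is stated, so accuracy against plasma is at risk of upward bias if settings are chosen on those data. Under the assumed models the size is about 1 to 4 points of balanced accuracy for a tuned cut-off, and about 2 to 7 points if the best of four or five conditions is also taken. These figures rest on assumed separations, numbers of conditions and correlation, and on 50 true negatives.

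For the DBS antibody ELISA the point is narrower: the order of locking and testing is not stated. Nothing in the documents supports extending the concern to the primary endpoint or to vaccine effectiveness. It is a minor matter, worth correcting because the correction is cheap.

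**What to change.** 1. **Saliva and DBS PCR.** Choose one of two routes and state it. Either keep the kit or plasma cut-off with a handling protocol fixed in advance, or repeat the whole selection (handling condition and cut-off together) inside cross-validation or a bootstrap optimism correction. Correcting the cut-off alone would leave the bias from choosing among conditions untouched. Under the second route, report the corrected sensitivity and specificity with confidence intervals as the result.
2. **DBS antibody ELISA.** Lock the protocol and cut-off in a dated version of the Lab Analysis Plan after the ideSHi and pilot work, and before testing the 50 main-study participants under Biological sampling and the 50 + 50. Use those two sets for evaluation only. The ideSHi material should not set the cut-off by itself, because it is described as patients' serum, not capillary blood, and no negatives are named.

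The cost is wording in three sections of the protocol and in the Lab Analysis Plan, a little more analysis, and slightly less favourable accuracy figures. It calls for no specimens beyond those already planned, and the 50 + 50 need not be split.

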The effectiveness of a HEV-vaccine needs to be tested in a population with high endemicity to be conducted in a reasonable time period. Bangladesh is suitable for this type of study. Recently, it has been estimated that there are 1000 HEV-related maternal deaths per annum in Bangladesh alone (Labrique, 2012). This study will be conducted at Matlab, a field study area of the International Centre for Diarrhoeal Disease Research, Bangladesh (icddr,b). A recent study from this region showed that 22% of the population had been previously infected with HEV, and the incidence of seroconversion was 60 per 1000 person years (Labrique, 2010). Further, we have documented baseline data on HEV incidence and burden of disease in Bangladesh (Gurley, 2012, Labrique, 2012). Importantly, the epidemiology of HEV in Bangladesh is similar to other parts of South Asia, so results from the trial will be relevant for the estimated 1.5 billion South Asians at risk for HEV. Genotype 1, which is homologous to the Chinese vaccine antigen, dominates in Bangladesh so there is reason to believe that Hecolin will be as effective in Bangladesh as in the Chinese trial where genotype 4 is endemic. Matlab has been the site for many successful large-scale vaccine field trials in the past, including trials of oral cholera vaccine ([name], 1991) and rotavirus vaccine (Zaman, 2010), in addition to several large-scale studies of pregnancy (Persson, 2012). Matlab is thus suited for undertaking the trial described in this protocol.

Bangladesh has historically been a pioneer in vaccine introduction, and the close partnership between icddr,b and the Bangladesh government has played an important role in the deployment of new generation vaccines into public health programs. The government recognizes the seriousness of HEV disease, especially in pregnant women, and has expressed interest in the potential introduction of HEV vaccine in its public sector programs, as the projected impact will be high. However, the feasibility of the delivery of the HEV vaccine and acceptance of vaccine by the users are not known.

Summary of findings from previous studies

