The vaccine has been shown to be safe and highly efficacious against HEV disease in a large phase III trial in China with over 100,000 participants (100% after 3 doses of vaccine, 95% CI: 72.1-100.0), where it is commercially manufactured and licensed sale (Zhu, 2010). The majority of cases in this trial were due to genotype 4, indicating that the vaccine was able to confer genotype-heterologous protection. The vaccine was highly immunogenic with seroconversion rates of 98-100% among vaccinees (Zhang, 2014). The study did not provide sufficient data (not powered) to show efficacy in preventing HEV disease during pregnancy. Pregnant women are most vulnerable to HEV-infection and have the greatest impact of an effective vaccine.

Summary of known and potential risks

In phase 1, 2 and a large phase 3 study conducted by the manufacturer, preclinical toxicity of HEV239 was assessed and Hecolin was well tolerated and safe for use in healthy adults. AEs were mainly local with pain, swelling and itching at the injection site. The rate of AEs was similar in the study groups and the placebo groups (receiving a Hepatitis B vaccine). AEs of grade 3 or more were reported only very rarely, and include injection site swelling, fever and headache.

An extended follow-up study from the phase 3 study collecting data on safety for up to 4.5 years after the first vaccine dose, showed the number of reported SAEs (4792 vs 4667; $p=0.179$) and the number of participants with one or more SAE (4602 vs 4490; $p=0.221$) to be comparable between the vaccine and placebo groups. None of the SAEs was judged by the principal investigator (who reminded masked to treatment assignment) to be related or possibly related to the hepatitis E vaccine (Zhang, 2015).

Phase III retrospective cohort study - pregnant women

There are limited data on safety of Hecolin® on maternal and fetal outcomes following use during pregnancy.

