Pretesting Before proceeding a large scale trial, we will perform pretesting of the study. We will look mainly at/on the safety and also immunogenicity of this vaccine with this small sample size. This will be done outside of the MCH-FP area but within the HDSS area. The sample size for the pretesting phase will be 25 female and 25 male from the HEV and HBV group respectively (estimated assuming 70% seroresponse in vaccine group vs. 10% in control, $p < 0.05$, 2 tailed, 0.9 power). The sample will be randomly selected among nonpregnant women aged 16-39 years and male will be randomly selected from the age group of 16-39 years. We will observe each participant for 30 minutes after each vaccination. After each dose field worker will visit daily for 7 days at their homes enquiring about any untoward events. Blood will be collected before vaccination and 1 month after the second dose. Process for determining immunogenicity will be same as described in the protocol.

We want to find out the strength and longevity of the immune reaction to a two-dose schedule compared to the standard three-dose schedule of the vaccine for the pilot study. We will collect one blood sample

(maximum 3ml) from all participants of pilot study (100) to determine the immune response and an additional 9 ml blood from the 10 persons previously selected to assess the cellular response approximately 2 years after first vaccination.

To better understand the persistence of immunological responses 2 years (24 to 35 months) after the last dose of the vaccine we will do a sub-study under this main study. We will sequentially enrol for this add-on study from the list of original enrollment and identify eligible participants who received 3 doses of vaccine and completed follow up 2 years (24 to 35 months) and also who received 1 or 2 doses of vaccine (incomplete schedule). We will include total 1,760 (440 participants in each group) HEV vaccine study participants for this sub-study among those who are 1) HEV seronegative at baseline and received HEV vaccine, 2) those who were HEV seropositive at baseline and received HEV vaccine, 3) who were HEV seropositive at baseline and received HBV vaccine, 4) participants who are HEV seronegative at baseline and received HBV vaccine (pure control group).

Enrolment

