The study is sponsored by GLOBVAC funds from the Norwegian Research Council.

Trial insurance

As a standard insurance policy of clinical trails of icddr,b.

Publication policy

Upon study completion and finalization of the study report the results of this study will be submitted for publication.

The results of this study will also be submitted to the Competent Authority and the Ethics Committee according to national regulations.

All personnel who have contributed significantly with the planning and performance of the study may be included in the list of authors.

Sample Size Calculation and Outcome (Primary and Secondary) Variable(s)

Clearly mention your assumptions. List the power and precision desired. Describe the optimal conditions to attain the sample size. Justify the sample size that is deemed sufficient to achieve the specific aims.

Sample size: The sample size for the study has been calculated based on the following assumptions (data from Matlab HDSS and HEV research studies). The goal will be to estimate total vaccine protection in a per protocol analysis. Women 16-39 years constitute 20% of the general population, and 22% will be HEV seropositive at baseline (we assume that these women will be protected against HEV

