infection); post dose 3 follow up will range from 22-28 months (average 25 months). During post dose 3 follow up, 16% of women (followed over a mean of 16 months) will become pregnant and will reach term before the end of surveillance; an additional 9% of women (followed over a mean of 9 months) will be followed for an average of half full term (4.5 months); this predicts that 20% of the dose 3 recipients will have "completed" pregnancies, 3806 are expected to become pregnant after dose 3 and 3073 to be followed to term (follow up of the remaining pregnancies will be right censored by termination of follow up); 6% of seronegative pregnant women will become infected during pregnancy of which 35% of infections will be symptomatic; the protective efficacy of a 3-dose regimen of HEV vaccine against symptomatic infections is $\geq 95\%$, $p < 0.05$ (2 tailed); there will be 15% loss of person-time due to migration out; 10% of women will not be included due to pregnancy at baseline, the refusal rate will be 5%; another 10% will not complete 3 doses for other reasons (e.g intercurrent pregnancy) and the design effect will be 2. To achieve 0.8 power, we will need a sample size of 20,745 women to be enrolled at baseline (60% are assumed to receive all 3 doses which takes into account of 10% baseline pregnancy, 5% refusal, 15% loss to follow up and 10% for other reasons e.g. intercurrent pregnancy), derived from a total population of 116,377, which can be assembled from the MCH-FP area population in Matlab (Labrique et al, 2010; icddr,b 2012). Although not a primary outcome, our study will have 90% power to evaluate $\geq 95\%$ protective efficacy against HEV disease among non-pregnant women. Although the ultimate goal of any future vaccination campaign would be to prevent maternal and perinatal mortality, the sample size for our study will not be able to directly evaluate these outcomes with adequate power due to the low perinatal, maternal death ratios in Matlab. However, given the substantial evidence linking maternal and perinatal mortality to HEV disease in pregnancy, demonstration of vaccine protection against confirmed HEV disease in pregnancy will provide strong evidence that vaccination will likely prevent maternal and perinatal deaths. The table below shows the results of the sensitivity analysis of sample size with different assumptions, maintaining 0.8 power and a design effect of 2.

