We will measure total vaccine protection as our primary objective in a per protocol analysis of three-dose vaccine recipients, using analytic methods to adjust for the design effect of cluster randomization (Halloran, 1997; Donner 2000). In this analysis we will compare the incidence of confirmed HEV disease in pregnant women who have been recipients of a complete three dose regimen of HEV vaccine or HBV vaccine and in whom the HEV disease episode begins at least 14 days after the third dose of vaccine. We will attempt to assess the indirect vaccine protection (defined as protection of non-HEV vaccinees in HEV vaccine clusters) and overall vaccine protection (defined as protection of all members of HEV vaccine clusters relative to all members of HBV vaccine clusters), but are aware that our trial may not be adequately powered for these analyses. Adverse events, immune responses to vaccines, and other outcomes will employ tests appropriate for comparison of categorical and dimensional outcomes, adjusted for the design effect of cluster randomization. All statistical tests will be evaluated at $P < 0.05$, two tailed.

In one main analysis (**Analysis 1**), we will compare waning of serum titers of IgG anti-HEV antibodies elicited by the third dose of HEV, measured 2 years (24 to 35 months) later after dose 3, among those who are 1) HEV seronegative at baseline and received HEV vaccine, 2) those who were HEV seropositive at baseline and received HEV vaccine, 3) who were HEV seropositive at baseline and received HBV vaccine, 4) participants who are HEV seronegative at baseline and received HBV vaccine (pure control group).

In a second main analysis (**Analysis 2**), we will also compare the decline in the attributable percentage of HEV seropositive (% HEV vaccinees who are IgG HEV serum antibody seropositive minus % of HBV vaccinees who are HEV seropositive) among those who are HEV seronegative at baseline until two years after the third dose. In secondary analyses we will conduct similar analyses of serum IgG subclass anti-HEV antibodies, as well as similar analyses among persons who only received only the first dose, or only the second dose of either vaccine or two doses due to receipt of incomplete vaccine regimens.

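### Persistence Analysis 2 tracks the fall in a difference of seropositive percentages, and that difference falls as controls are naturally infected even if no vaccine antibody is lost

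*Combined protocol and SAP*

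**What the plan says.** Specific Objectives lists a secondary objective: "To analyze the persistence of vaccine induced serum antibody responses". Statistical Analysis gives two main analyses for it. Analysis 1 compares the waning of IgG titres across four groups defined by baseline serostatus and vaccine received. Analysis 2, restricted to women seronegative at baseline, looks at how far a between-arm contrast has dropped by two years after dose 3. The contrast is written as "HEV vaccinees who are IgG HEV serum antibody seropositive minus % of HBV vaccinees who are HEV seropositive", both terms being percentages. The same approach carries over to IgG subclasses and to women with incomplete regimens.

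Other relevant statements:

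- 1.2 Rationale for the Study, on local infection: "the incidence of seroconversion was 60 per 1000 person years".
- Sample size: "22% will be HEV seropositive at baseline" and "the design effect will be 2".
- Summary of findings from previous studies: "seroconversion rates of 98-100% among vaccinees".
- Pretesting, which also describes the persistence sub-study: "We will include total 1,760 (440 participants in each group) HEV vaccine study participants for this sub-study".
- Blood is drawn at baseline, one month after the last dose (month 7 for a full course) and 24 to 35 months after dose 3 (months 30 to 41).

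No expected value, effect size, power or decision rule is given for Analysis 2.

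**The concern.** Subtracting the control percentage removes natural infection only if infection adds the same amount to both arms. Here it cannot. By selection the controls begin at 0%, and section 1.1.1 says that IgG marks recent or remote exposure, so each natural infection can move a control into the positive group. Almost every HEV vaccinee is already positive, so infection has nearly nothing to add in that arm. The subtracted figure grows while the other stays near its ceiling.

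At one time point the difference is a valid measure of excess seropositivity due to vaccination. Its decline mixes two things: loss of vaccine antibody and infection of controls. The plan gives no rule for separating them. Vaccine antibody that persists perfectly would appear to wane, by an amount that depends on local HEV incidence. One of the two main analyses for the persistence objective could then mislead, and the error would repeat in the subclass and incomplete-regimen analyses.

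**Working it through.** The plan states no figure for Analysis 2, so there is none to reproduce. The check asks how far the planned measure would fall if no vaccine antibody were lost.

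**Model.** Let V be the share of vaccinees with vaccine antibody and C(t) the seropositivity of baseline-seronegative controls. If vaccinees without vaccine antibody are infected at the control rate:

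- pV = V + (1 − V)C and pC = C
- difference = pV − pC = V(1 − C)
- fall between t1 and t2 with V constant = V[C(t2) − C(t1)]

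Control seropositivity, with infection rate λ and seroreversion rate μ per year, is C(t) = λ/(λ+μ) × (1 − exp(−(λ+μ)t)), t counted from day 0. The times are 7 months (the only earlier sample after dose 3), 30 months and 41 months.

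**Cases.**

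- A: λ = 0.06 (protocol incidence), μ = 0.
- B: λ = 0.06, with μ = 0.06 × 0.78/0.22 = 0.213, so that 22% is the equilibrium prevalence.
- C: μ = 0 and λ = −ln(0.78)/27.5 = 0.0090, the lifetime-average rate implied by 22% seropositivity at an assumed mean age of 27.5.

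The seroreversion rates, the equilibrium and the mean age are assumptions; the documents do not give them.

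**False fall, vaccinees held at 99% positive.**

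| Case | Controls at month 7 | Controls at 24 / 35 months after dose 3 | Fall in difference (points) |
|---|---|---|---|
| A | 3.4% | 13.9% / 18.5% | 10.5 / 15.1 |
| B | 3.2% | 10.9% / 13.3% | 7.6 / 10.1 |
| C | 0.5% | 2.2% / 3.0% | 1.7 / 2.5 |

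Using V(1 − C) with V = 0.99 barely changes this: A becomes 10.4 / 14.9. For C, assumed mean ages from 33 down to 22 give 1.4–2.1 / 2.1–3.1 points.

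**Plausibility of A.** At 0.06 a year without seroreversion, 22% is reached in −ln(0.78)/0.06 = 4.1 years, and 1 − exp(−0.06 × 16) = 62% would be positive at age 16. That does not fit the protocol's 22%, so A is the upper of these three cases. It is not a hard ceiling: the sample-size figure of 6% infected per pregnancy, taken as nine months and applied to all women without seroreversion, would give 13.9 / 19.9 points.

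**Size against sampling error.** Take 440 women per group and the design effect of 2 stated for the primary sample size, used here as an assumption.

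- Time points treated as independent: SE = √{2 × [2 × 0.99 × 0.01 + C1(1 − C1) + C2(1 − C2)]/440}. For A at 24 months this is 2.80 points, and z = 10.49/2.80 = 3.7. In full, z is 3.7 / 5.0 in A, 2.9 / 3.7 in B and 1.2 / 1.6 in C.
- Paired within woman, with only controls changing status: 5.1 / 6.3 in A, 3.8 / 4.4 in B and 2.0 / 2.4 in C.

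**Rescaled measure.** (pV − pC)/(1 − pC) = V(1 − C)/(1 − C) = V. With pV held at 0.99 it stays between 98.8% and 99.0% in every case and at every time.

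**Stress test.** Take case A with a true 10% loss of vaccine antibody (99.0% to 89.1%, or 9.9 points) and no infection at all in vaccinees who lack antibody, the worst failure of the model's assumption. At 24 months the rescaled measure is (0.891 − 0.139)/(1 − 0.139) = 87.3%. At month 7 it is (0.990 − 0.034)/(1 − 0.034) = 99.0%, so it falls 11.6 points. The planned difference goes from 95.6 to 75.2, a fall of 20.4 points.

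**The case against.** The plan uses the word waning only for Analysis 1. Analysis 2 can be read as a description of how much more often vaccinated women remain seropositive than unvaccinated women, and as a description it is coherent. But it is labelled a main analysis, it measures a decline, and it serves an objective about persistence of the vaccine-induced response. Readers will take the decline as waning unless told otherwise.

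The top of the range rests on zero seroreversion and on sampling every woman at the far edge of the window, although Analysis 2 speaks of two years. That stands. B is the only case matched to both the 60 per 1000 and the 22%, and it gives 7.6 to 10.1 points. B in turn assumes that natural antibody is lost at 21% a year while vaccine antibody is not lost at all. In C the effect is small and may not be detectable.

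The z-values are also soft. The design effect was set for another analysis, the paired version ignores variation in the HEV arm, and the sub-study also admits women with one or two doses, so 440 three-dose women per group is not assured. No decision rule is attached to the decline.

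There are partial safeguards. Seroconversion at month 7 is compared between arms, Analysis 1 follows the seronegative control group, and both percentages must be computed to form the difference. However, nothing requires the late percentages to be reported, and Analysis 1 concerns titres.

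Finally, the rescaled measure has its own assumption, which indirect protection in HEV villages would break. The stress test shows that it can be biased, but far less than the planned difference.

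**Conclusion.** The concern holds. With vaccinees near 100% and controls starting at 0%, the planned difference declines without any loss of vaccine antibody. The false part is about 2 to 15 points over the sampling window in the three cases, and about 8 to 10 points in the case matched to both protocol figures. The direction follows from the protocol's own inputs under a constant infection rate. The size depends on local incidence and seroreversion, and whether it reaches significance depends on the case. This should be corrected. It concerns a secondary objective, and Analysis 1 and the primary endpoint are not affected in this way.

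**What to change.** Amend Analysis 2 so that the decline in the simple difference is not the measure of waning. Report, with intervals that allow for village clustering:

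1. the change from month 7 to 24–35 months after dose 3 in (pV − pC)/(1 − pC);
2. seroreversion among HEV vaccinees who were positive at month 7;
3. the percentage seropositive in each arm at each time.

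State that (1) assumes vaccinees without vaccine antibody are infected at the control rate, and that natural infection of vaccinees can hide some seroreversion in (2). The simple difference may stay as a description of excess seropositivity at each time. Make the same change in the IgG subclass and incomplete-regimen analyses.

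The cost is SAP wording and minor programming on samples already planned, a slightly wider interval, and one assumption to declare.
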